- a) **BREATHE delivery mode**: We will create 1 adaptation of BREATHE-T1D. The format will be BREATHE-T1D telehealth. This approach will use a telehealth delivery platform, Zoom, currently in use by the telehealth division and CNH providers for a variety of behavioral/medical treatments. Zoom allows for groups to occur via video so that each member can see the others, mimicking the experience of an in-person group. We anticipate that BREATHE-T1D manual/teen workbook will require minimal-to-no modifications in order to deliver the program via Zoom.
- b) **Finalize standard operating procedures**: Written standard operating procedures, with accompanying checklists, will be finalized for all aspects of the pilot RCT. An amendment will be submitted to the IRB, as needed, based upon protocol revisions and adaptations for BREATHE-T1D telehealth and HealthEd-T1D. All research staff will be trained in protocols, complete/update CITI trainings in responsible conduct of research, and prepare/test REDCap databases for surveys and data management.
- c) **Train interventionists**: Interventionists will be master's or doctoral level clinicians who have experience working with teens with T1D. Interventionists will participate in a comprehensive 3-day training to learn BREATHE-T1D and HealthEd-T1D. Training will be led by Drs. [name] (PI), [name] (Co-I), and [name] (Co-I). Drs. [name] and [name] have expertise in behavioral T1D interventions. [name] has expertise in BREATHE delivery and training/supervision. Training will be conducted virtually, and it will include presentations of theoretical/empirical background, review of BREATHE-T1D and HealthEd-T1D intervention manuals/teen workbooks, modeling of session elements, and role-play using mock-groups. Telehealth protocols and delivery methods will be practiced.

3. **Phase 3: Carry out Pilot and Feasibility RCT**:

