- a) **Participants**: We will recruit a total $N=40$ participants for $n=20$ in each arm of the intervention from the ~700 adolescents seen through the CNH T1D clinic annually]. Participants will be included on the basis of the following criteria: (i) age 12-17y, (ii) T1D, with at least 1-year duration of illness, (iii) negative affectivity, defined as clinically elevated scores (T-score ≥ 55 indicating at least mild depression/anxiety symptoms on either the PROMIS short form-depression and/or anxiety scales), similar to criteria used in our previous studies in this patient population,⁶⁷ and recommended for use in clinic screening procedures in youth with T1D,^{68]} (iv) English-speaking, (v) no cognitive or developmental delays which would interfere with their ability to participate in the study, and (vi) have no other serious medical conditions (e.g., cystic fibrosis, cancer). Participants with Spanish-speaking parent will not be excluded; consent and parent surveys will be translated into Spanish and an interpreter will be utilized for delivery of consent. Participants will not be excluded based upon insulin regimen or method of measuring blood glucose. Participants will not be excluded based on receiving outside psychological support, but treatment outside of the study will be carefully tracked and controlled for in analyses.
- b) **Recruitment**: Participants will be recruited using a variety of approaches that have been highly successful in previous studies conducted by Drs. [name] (PI) and [name] (Co-I) in youth with T1D. Success of these approaches for the particular pilot RCT will be tracked to inform a future efficacy trial. Strategies will include: (i) direct mailings, emails, and phone calls to participants who, based upon an electronic medical record review, appear to be eligible, based upon age, health status/diagnoses, and (ii) in-person approach of teens and parents at T1D clinic appointments who are in the target age range. Potentially interested participants will be screened for depression and anxiety and will be invited to enroll if they meet the criterion for elevated (T-score ≥ 55) depression and/or anxiety. Although recruitment feasibility must be tested for the current 2-way intervention protocol, our team has a strong history of

recruitment/retention for clinical trials in youth with T1D, with a recruitment rate of 71% in a prior trial targeting an adolescent T1D population.⁶⁹

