- c) **Baseline assessment:** Following the pre-screen, participants who are interested and eligible will be met at the clinic most convenient for them. The endocrinology division at CNH sees patients across 6 different outpatient clinics across Maryland, Virginia, and DC. Baseline assessments will be done via telehealth for maximum flexibility for participants or can be done in person to coincide with a quarterly endocrinology healthcare visit. At this telehealth visit, they will complete a virtual informed consent process, complete baseline questionnaires, and participate in an orientation visit, which we have found in previous studies results in strong retention and participation rates. They will receive a \$50 ClinCard for completion of this assessment and study-specific retention items (e.g., study logo water bottle).
- d) **Group participation:** A computerized randomization sequence will be created by the data manager in randomly permuted blocks. After completion of baseline assessments, allocation will be performed by the study coordinator using REDCap, which conceals the sequence. Teens will be randomized to BREATHE-T1D telehealth or HealthEd-T1D. As shown in **Table 1**, we will aim for $n=5$ youth/group and interventions will be run in parallel. If scheduling is difficult, we will recruit up to 12 for each of the first two cohorts and allow for two groups of 3 per intervention condition in order not to delay interested candidates and have enough per group. We will still maintain an overall n of 40, adjusting the numbers in the final cohort based on what we have in cohorts 1 and 2. Based upon our base BREATHE and HealthEd manuals, we anticipate that group duration will be ~6 consecutive weeks, 1-hour/week during non-school hours, with potential for duration/frequency modifications based on the adaptation phase.

Table 1. Estimated timeline for pilot and feasibility RCT of $N=40$ adolescents with T1D

Quarter 1	Quarter 2	Quarter 3	Quarter 4
Recruitment Cohort 1 $n=10-12$	Recruitment Cohort 2 $n=10-12$	Recruitment Cohort 3 $n=16-20$	
Baseline assessment Cohort 1	Baseline assessment Cohort 2	Baseline assessment Cohort 3	
Cohort 1 BREATHE-T1D telehealth $n=5-6$ HealthEd $n=5-6$	Cohort 2 BREATHE-T1D telehealth $n=5-6$ HealthEd $n=5-6$	Cohort 3 BREATHE-T1D telehealth $n=8-10$ HealthEd $n=8-10$	

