There will be 90 total participants across both phases of study (3 diabetes team providers, 7 adolescents with T1D for the intervention development qualitative feedback, and 40 adolescent and caregiver dyads for the feasibility trial). Diabetes team providers ($n=3$) will be interviewed to provide feedback regarding the adaptation of BREATHE for use with adolescents with T1D. We will recruit a total $N=40$ participants for $n=20$ in each arm of the intervention. Participants will be included on the basis of the following criteria: (i) age 12-17y, (ii) T1D, with at least 1-year duration of illness, (iii) negative affectivity, defined as clinically elevated scores (T-score ≥ 55 indicating at least mild depression/anxiety symptoms on either the PROMIS short form-depression and/or anxiety scales) (iv) A1c $>7.5\%$, (v) English-speaking, (vi) no cognitive or developmental delays which would interfere with their ability to participate in the study, (vii) are able and willing to complete questionnaires and intervention via the internet, (viii) do not have severe depression or active or recent (within the past two months) suicidal ideation and (ix) have no other serious medical conditions (e.g., cystic fibrosis, cancer). Participants with Spanish-speaking parent will not be excluded; consent and parent surveys will be translated into Spanish and an interpreter will be utilized for delivery of consent. Participants will not be excluded based upon insulin regimen or method of measuring blood glucose. Participants will not be excluded based on receiving psychological support outside of the context of the study, but treatment outside of the study will be carefully tracked and controlled for in analyses. The study will be nonselective in its recruitment and enrollment with respect to gender, race, and ethnicity.

F. Human Subjects

Adolescents and a primary caregiver will be recruited from the Child and Adolescent Diabetes Program at CNMC. Adolescents between the ages of 12-17 will be studied to capture both early and later development of eating disorder and disordered eating symptoms.

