Participants will be recruited using a variety of approaches that have been highly successful in previous studies conducted by Drs. [name] (PI) and [name] (Co-I) in youth with T1D. Success of these approaches for the particular pilot RCT will be tracked to inform a future efficacy trial. Strategies will include: (i) direct mailings, emails, and phone calls to participants who, based upon an electronic medical record review, appear

to be eligible, based upon age, health status/diagnoses, A1c and (ii) in-person approach of teens and parents at T1D clinic appointments who are in the target age range. Potentially interested participants will be screened for depression and anxiety using the PROMIS scales and will be invited to enroll if they meet the criterion for elevated (T-score ≥ 55) depression and/or anxiety.

G. Risks and Side Effects:

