There are no known psychological risks to subjects when providing feedback via qualitative interview or when filling out standardized psychological questionnaires. However, the questionnaires may contain questions that make the subjects feel uncomfortable in that they ask about their physical and psychological health. Additionally, we will be recruiting participants with elevations on measures of depression and/or anxiety. For participants by self-report responding that they are experiencing a clinically significant level of anxiety OR depressive symptoms (using the PROMIS short form – T > 55 cutoff for depression and for anxiety subscales), we will follow a protocol that has been effective in our prior studies. Additionally, adolescents report on disordered eating behaviors, including risky behaviors such as insulin withholding. The DEPRS will be screened for clinical cutoff and specifically for endorsing either of the two items that ask about insulin withholding. Specifically, all forms will be reviewed by the clinical research assistant within 24 hours of completion or in real time for screenings taking place in clinic or via zoom (and flagged if either the depression or anxiety scores are above the clinical cutoff (T-score > 55) or if the DEPRS is above the clinical cutoff AND/OR either of the insulin withholding items are endorsed). If the score is above the clinical cutoff or the insulin withholding items are endorsed, the study team will notify the family both that they are eligible for participation in the study, and also reminded of additional referrals for care, including the in-house diabetes psychologist and other community referrals. The PROMIS measures do not assess for suicidal ideation, and we will not be assessing this specifically given that it is outside of the scope of this trial. However, if suicidal ideation or intent is suggested during the course of any study interactions, the PI [name], a licensed child clinical/pediatric psychologist, will be informed immediately via cell phone, and outreach to the parent and teen will be made. All research staff interacting with patients (e.g., research coordinator, research assistants) will be trained in our lab's risk assessment procedures. If deemed necessary, the teen will be referred for immediate mental health evaluation at the CNH Emergency Department. Our team of T1D psychologists maintains written protocols for all cases that necessitate a possible breach of confidentiality and for handling concerns that may arise such as suicidal ideation or self-harm. As we have done successfully in prior studies, we will monitor ongoing parent and teen reporting of the use of mental health support outside of the study either via usual care (e.g., seeing the in-clinic psychologist) or outside therapy/consultation or other behavioral health services. Paralleling national trends, most teenagers with T1D, even when screened and referred, do not seek regular therapy due to a variety of barriers. Thus, the interventions being offered, including the control condition, will likely offer more support and monitoring than adolescents would otherwise receive, even when they screen positively for depression/anxiety in diabetes clinic.

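### Section E(viii) bars severe depression and recent suicidal ideation, but no severity threshold is given and Section G says ideation will not be specifically assessed

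*Combined protocol and SAP*

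**What the plan says.** Section E lists nine criteria for the feasibility trial. Criterion (viii) requires that participants "do not have severe depression or active or recent (within the past two months) suicidal ideation". Criterion (iii) requires a PROMIS depression and/or anxiety T-score of at least 55, described as at least mild symptoms.

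Sections D.3b and F describe recruitment: a review of the electronic medical record (age, health status and diagnoses, and in F also A1c), approach in clinic, and PROMIS screening. Those screened "will be invited to enroll if they meet the criterion for elevated" depression and/or anxiety, with the same cutoff of 55.

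Section G describes what happens to the forms. On ideation it says: "The PROMIS measures do not assess for suicidal ideation, and we will not be assessing this specifically", giving as the reason that this lies outside the trial's scope. A response is triggered "if suicidal ideation or intent is suggested during the course of any study interactions": the PI is told at once, the family is contacted, and the teen is sent for emergency evaluation if needed. When a score is above the cutoff or an insulin-withholding item is endorsed, "the study team will notify the family both that they are eligible for participation in the study", and the family is reminded of referral options.

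**The concern.** The trial recruits minors because their depression or anxiety scores are elevated, so (viii) is the criterion that keeps the highest-risk teens out of a group telehealth programme. An exclusion with a two-month look-back needs a source of information, and an exclusion for severity needs a threshold. If neither is specified, staff following the protocol can enrol a teen whom the protocol says should not be enrolled, and two staff members could classify the same PROMIS score differently.

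What is at stake is participant safety and consistent application of an eligibility rule. The count of eligible teens is also the denominator of the Aim 2 recruitment target (at least 80% of eligible teens enrolling after screening), though the documents do not show how far that figure would move.

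**Working it through.** No arithmetic applies: the protocol states no figure on this point, and none can be derived. The check is to read every section on eligibility, screening, measures and risk for two things: a source of information on ideation, and a definition of severe.

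**Ideation**

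1. *Exclusion:* Section E(viii) covers current ideation and ideation in the last two months.
2. *Instruments:* the screening tool is PROMIS, which Section G says does not cover ideation. No other measure in Table 2 or the Aim 2 table is described as covering it.
3. *Record review (D.3b, F):* looks at age, health status and diagnoses, and A1c. Ideation and the two-month window are not mentioned.
4. *Pre-screen (D.3c):* mentioned only in passing: "Following the pre-screen, participants who are interested and eligible will be met at the clinic most convenient for them". Its content is not described.
5. *Procedures (D.2b):* "Written standard operating procedures, with accompanying checklists, will be finalized for all aspects of the pilot RCT". A check could sit there, but none is named.
6. *Section G:* says that ideation will not be specifically assessed. The sentence is not limited to the period after enrolment, and it comes shortly after the text on reviewing screening forms.

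Steps 2 to 5 leave room for a check without describing one, and step 6 points against one. What remains is incidental knowledge: ideation already in the chart, reported by a parent, or disclosed before enrolment.

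**Severe depression**

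1. *Exclusion:* Section E(viii), with no definition.
2. *Only threshold in the documents:* a PROMIS T-score of 55, used as a lower bound for inclusion.
3. *Invitation rule (D.3b, F):* elevated score leads to invitation, with no upper limit.
4. *Available data:* the PROMIS depression score is collected at screening, so a ceiling could be applied at once. None is stated, and no charted diagnosis is named as an alternative.

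The two halves therefore fail differently. The severity half lacks only a cut-point on data already in hand. The ideation half lacks a described source.

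**The case against.** The strongest reply is that the exclusion is not empty. A teen whose ideation is charted, reported or disclosed before enrolment can still be turned away under E(viii). All staff who deal with patients are trained in risk assessment. Section G also refers to a protocol used in the team's prior studies for teens above the cutoff, and to written protocols held by the diabetes psychologists for suicidal ideation and self-harm. This stands, and it limits the claim: the public protocol describes no systematic check, which is not proof that the site has none. A reader might infer that the protocol has no safeguard at all; the documents do not support that. But none of these procedures is said to determine eligibility.

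A reader might also take Section G's notice as a rule that makes every teen above the cutoff eligible, overriding E(viii). That reads too much into it. Taken literally, an endorsed insulin-withholding item alone would confer eligibility, and age, diabetes duration and A1c would be ignored. It is a loosely worded notification step, and it needs only a wording alignment.

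Third, severe need not mean a PROMIS score; it could mean a charted diagnosis. That is fair, and either definition would do, but the protocol has to choose one.

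Finally, D.3a lists six of Section E's nine criteria and omits (viii). This might be read as a second, conflicting eligibility rule. Section E contains everything in D.3a and adds to it, so the shorter list is incomplete and does not conflict.

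**Conclusion.** The point holds and should be fixed. Section E states an exclusion that Section G's decision not to assess ideation largely defeats, and the severity part of the same criterion has no threshold. Followed as written, the plan can enrol teens whom its own safety criterion bars.

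The size cannot be given. The documents report no rate of ideation or severe depression in this population and no rate at which either would come to light before enrolment, so any count among the 40 would rest on assumed inputs. The consequences are bounded on two sides: Section G's form review within 24 hours or in real time, referral reminders, PI notification and emergency referral reduce harm once a problem surfaces, and no efficacy analysis is planned, so no treatment comparison of efficacy is affected.

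The conclusion assumes that procedures not described in the protocol do not already contain an eligibility check for ideation. If they do, the remedy reduces to describing that check and correcting Section G's sentence; the severity definition would still be needed unless those procedures also supply it.

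**What to change.** 1. **Define severe.** State the PROMIS depression T-score, or the charted diagnosis, that counts as severe, and apply it at screening in D.3b and F.
2. **Give the ideation exclusion a source.** Add a check for ideation in the last two months to the existing record review and pre-screen, and amend Section G's sentence to agree. Whether to question teens directly is for the clinical team and the IRB. If they decide against it, keep the exclusion and reword E(viii) as ideation known from record review, parent report or disclosure. Deleting it would make teens with known recent ideation eligible.
3. **Align Section G's notice.** Families should be told that the teen is eligible only once all of Section E's criteria are confirmed.

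Repeating Section E's full list in D.3a would be tidy but is optional.

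The cost is a short protocol amendment with IRB review and a little more chart-review time. Direct questioning would cost more: consent is taken at the baseline visit, after the pre-screen, and some forms may be reviewed up to 24 hours after completion, so asking minors about ideation at that stage would need prompt clinician cover through the existing PI-notification pathway. Sample size and analysis are unchanged.

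### The safety section flags PROMIS scores above 55 while entry is at 55 or above, so a teen at exactly 55 is eligible but, read literally, not flagged or reminded of services

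*Combined protocol and SAP*

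**What the plan says.** **Entry.** Section D, Phase 3, item a (Participants) defines the symptom criterion as "negative affectivity, defined as clinically elevated scores (T-score ≥ 55 indicating at least mild depression/anxiety symptoms" on the depression and/or anxiety short form. Section E (Study Population) repeats it: "T-score ≥ 55 indicating at least mild depression/anxiety symptoms on either the PROMIS short form-depression and/or anxiety scales". Section D, Phase 3, item b (Recruitment) and Section F (Human Subjects) both say that screened teens will be "invited to enroll if they meet the criterion for elevated (T-score ≥ 55) depression and/or anxiety". A score of 55 is included every time.

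**Flag and referral.** Section G states the cutoff twice, both times strictly. The protocol for elevated symptoms applies at the "T > 55 cutoff for depression and for anxiety subscales". On review, forms are "flagged if either the depression or anxiety scores are above the clinical cutoff (T-score > 55"). The eating survey gives a second, separate route to a flag, through its own cutoff or through either of its two items on withholding insulin. The sentence that follows makes the family notice depend on a score above the cutoff or an endorsed insulin-withholding item. The team will then "notify the family both that they are eligible for participation in the study, and also reminded of additional referrals for care", naming the in-house diabetes psychologist and community services.

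**The concern.** The trial recruits minors because they have elevated depression or anxiety symptoms, and Section G is where the protocol says what is done for them on that account. The set of teens it covers should contain every teen the entry rule admits. As written it leaves out the boundary value.

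What is at stake is narrow: a missed reminder of available services. Review of forms, the eating and insulin flags, escalation of suicidal ideation and staff risk training do not depend on the PROMIS cutoff. The target of at least 80% of eligible teens enrolling is not affected either, because entry is set at ≥ 55 wherever it is defined.

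There is also a practical conflict. The same Section G notice tells the family that the teen is eligible, so at exactly 55 Section F tells staff to invite a teen whom Section G, read literally, does not have them notify.

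**Working it through.** **Step 1: the two rules at the boundary.** Let M be the higher of the depression and anxiety T-scores.

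| M | Entry rule, M ≥ 55 (Sections D, E, F) | PROMIS flag rule, M > 55 (Section G) |
|---|---|---|
| below 55 | not met | not flagged |
| exactly 55 | met | not flagged |
| above 55 | met | flagged |

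The rules disagree only at M = 55. The plan gives no figure for how many teens this concerns, so there is none to reproduce.

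**Step 2: is the gap closed elsewhere?** The eating-survey cutoff and the two insulin-withholding items can flag a teen at 55, so the gap concerns teens with none of these. No section gives the referral reminder to every enrolled teen.

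**Step 3: how many teens?** The documents give neither the score distribution in screened teens nor the resolution of the T-scores. The following are therefore assumptions: the two scores are bivariate normal with common mean 50, 55 or 58, SD 10 and correlation 0.5 or 0.7. The share of PROMIS-eligible teens at the boundary is

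f = P(M rounds to 55) / P(M rounds to 55 or more) = [F(55 + h) − F(55 − h)] / [1 − F(55 − h)],

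where F(x) is the probability that both scores are at most x, with h = 0.5 for whole-number scores and h = 0.05 for one-decimal scores.

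Worked case, mean 50, correlation 0.7, whole numbers: F(54.5) = 0.5599 and F(55.5) = 0.6009, so f = 0.0410 / 0.4401 = 0.093. Over 40 teens this is 40 × 0.0933 = 3.7.

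| Assumed mean | f, whole-number scores | Expected of 40 | f, one-decimal scores | Expected of 40 |
|---|---|---|---|---|
| 50 | 9.1–9.3% | 3.6–3.7 | 0.95–0.97% | 0.38–0.39 |
| 55 | 5.8–6.2% | 2.3–2.5 | about 0.6% | 0.24–0.25 |
| 58 | 4.2–4.5% | 1.7–1.8 | 0.42–0.46% | 0.17–0.19 |

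(Ranges run over correlation 0.5 to 0.7.) With one-decimal scores the chance of at least one such teen among 40, 1 − (1 − f)^40, is 16% to 32%.

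**Step 4: allowance for the other flags.** Section C reports maladaptive eating in 25% of the site's earlier cohort. If that is taken as the eating-flag rate, independent of the PROMIS score, the counts are multiplied by 0.75: 1.2 to 2.8 of 40 for whole-number scores and 0.1 to 0.3 for one-decimal scores.

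**Step 5: after correction.** With Section G at M ≥ 55, the PROMIS-flagged set equals the PROMIS-eligible set and the count is zero by construction.

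**The case against.** The strongest reply is that Section G intends a single cutoff. Its notice tells the family that the teen is eligible, so it treats the flagged teen and the eligible teen as the same teen, and eligibility is ≥ 55 everywhere else. On that reading the symbol is a slip, and the harm would require staff to invite a teen at 55 while withholding the other half of one combined notice. This is probably what was meant. But the strict sign appears twice and the wording says above, so the text consistently states something else, and a form reviewer or an automated flag following it would apply > 55. A probable slip is a reason to correct the text.

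Second, written operating procedures and checklists are to be finalized (Section D, Phase 2, item b) and may state the right rule. They are not in the documents and do not amend the protocol. It does follow that whether any teen would actually be missed is unknown.

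Third, the counts rest on assumptions. This stands. The upper figure needs whole-number scores and the lowest assumed mean, with no allowance for other flags. Independence of the eating flag is doubtful too: Section C links negative affectivity to maladaptive eating, and its 25% comes from a cohort not selected for symptoms, so more teens may be flagged anyway. PROMIS is also repeated after the intervention and at 3 months, so some teens would be flagged later. That is a late reminder for some, and the calculation covers one occasion only.

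Fourth, these teens have the mildest qualifying scores, attend a clinic with a psychologist and meet trained clinicians weekly. This also stands, and it is why the point is minor.

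**Conclusion.** The mismatch is certain, because it is a direct comparison of the text: entry at 55 or more in Sections D, E and F, and flag and referral notice only above 55 in Section G. A teen at exactly 55 with no eating or insulin trigger is admitted but, as written, not flagged or reminded.

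The size is small and cannot be fixed from the documents. A reasonable range is 0 to about 4 of 40 teens. Most of that range depends on whole-number scoring, one-decimal scoring gives less than half a teen in expectation, and the count is zero if the short forms cannot return 55. The consequence is a missed or late reminder of services. Severity is minor.

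**What to change.** In Section G:

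- Change both strict statements of the PROMIS cutoff to T-score ≥ 55.
- In the flag sentence and the notice sentence, say at or above the clinical cutoff for the PROMIS scores. Name the PROMIS scores explicitly in the notice sentence, so that the eating survey's own cutoff is not altered by accident.
- Set any automated flag, and the matching checklist, to ≥ 55.

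Leave the entry criteria in Sections D, E and F as they are. The cost is a wording change in one section and at most a few more flagged forms and reminders. Eligibility, sample size and analysis do not change.
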